3.2 Analysis Populations

3.2.1 Enrolled Set

All participants who signed the informed consent form. The Enrolled Set will be used to summarize patient disposition.

3.2.2 Randomly Assigned to Study Intervention

All participants who were randomized. Participants will be analyzed according to the treatment to which they were randomized.

3.2.3 Full Analysis Set (FAS)

All randomized participants who received at least one dose of study intervention. In accordance with the intention-to-treat principle, participants will be included in the analysis according to the treatment to which they were randomized. For all efficacy analyses, FAS will be used.

3.2.4 Safety Analysis Set

All participants randomly assigned to study treatment who took at least one dose of study intervention and for whom any post-dose data are available. Participants will be analyzed according to the treatment which they actually received.

If a participant received study intervention from the wrong kit for only part of the treatment duration and then switched to another, the associated treatment group for that participant would be the treatment group that participant was randomized to.

The Safety Analysis Set will be used as the analysis set for all summaries for safety evaluation unless stated otherwise and for the analysis of the immunogenicity data.

3.2.5 Pharmacokinetic Analysis Set

The Pharmacokinetic (PK) Analysis Set will consist of all subjects in the FAS who received at least one dose of AZD8233 and who have evaluable PK data, with no important protocol deviations thought to impact on the analysis of the PK data.

The exclusion of any subjects or time points will be documented by the PK scientist, including the reasons for exclusion. The available concentration data for any participants excluded from the PK analysis set will be listed only. Concentration data for participants excluded from the PK analysis set will not be presented in the individual figures of concentration versus time plots.

The PK Analysis Set will be used to summarize the PK data and will be presented in accordance with the actual treatment received.

3.3 General Considerations

The following principles will be followed throughout the study:

- Continuous variables will be summarized by the number of non-missing observations, mean, standard deviation (SD), median, first and third quartiles, and the minimum and maximum as appropriate.
- Log-transformed continuous variables will be summarized in a similar manner. In addition, the relative change from baseline will be calculated by back-transforming the change from baseline of the logarithmic variable as necessary.
- Categorical variables will be summarized as counts (n) and percentages (%). Unless otherwise stated, percentages will be calculated using the relevant analysis set population total as the denominator. Percentages will not be presented for zero counts.
- Mean and medians will be rounded to one additional decimal place relative to the original data, the SD will be rounded to two additional decimal places, and the maximum, minimum and quartiles will be displayed with the same accuracy as the original data. 95% confidence intervals (CIs) will be presented to one more decimal place than the raw data. Percentages (proportion) will be rounded to one decimal place.
- Summaries will be provided by time point of assessment where appropriate. Where summaries are over time, study day will be calculated in relation to Day 1, the date of first dose of study treatment.

- Corresponding listings will be provided for all tabulated results unless stated otherwise. Any additional listings that are required will be described in the appropriate sections of the SAP.
- Statistical tests will be performed using two-sided test at a 5% significance level, if not explicitly stated otherwise.
- SAS® version 9.3 or higher will be used for all data analyses.

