3.3.3 Handling of Unscheduled Visits

Visits that fall outside the visit windows defined in the CSP will be classified as Unscheduled Visits. Unscheduled visits will be numbered sequentially with an increment of 0.1. For example, if two measurements are done in an unscheduled visit that occurs between Day 3 and Day 8, then these visits will be numbered UNS 2.1 and 2.2 in the order they occurred.

The values measured at unscheduled visits will not be included in the by-visit summary tables, they will be included in the overall summary tables (for abnormalities, minimum/maxima etc.) and will be presented in the listings.

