4.3.3 Clinical Laboratory, Blood Sample

4.3.3.1 Definitions and Derivations

In the assessments of hematology parameters, clinical chemistry and coagulation, the parameters to be summarized are listed in Appendix 7.2.

Clinical laboratory results will be assigned to analysis visits as described in Section 3.3.2.

Safety clinical laboratory results below the lower limit of quantification (LLOQ) for which the exact value cannot be determined will be replaced with the LLOQ.

After replacements of LLOQ, the change from baseline will be calculated for all post-baseline timepoints as the respective timepoint value minus the baseline value.

Based on the respective reference range indicators, the following flags will be applied to all laboratory assessments; 'Normal' (if the value is within the normal reference range), 'Low' (if the value is below the normal reference range) or 'High' (if the value is above the normal reference range).

eGFR

Subject's eGFR will be calculated from serum creatinine (SCr) concentration, according to the Japanese equation as follows:

$$\text{eGFR} = 194 \times \text{SCr}(\text{mg/dL})^{-1.094} \times \text{Age}^{-0.287} \times \alpha$$

where α is 1 for males and 0.739 for females.

Liver enzyme abnormalities

AST, ALT and TBL will be classified as follows:

AST and ALT:

- $<1.5 \times \text{ULN}$ (or below the LLOQ).
- ≥ 1.5 to $<3 \times \text{ULN}$.
- ≥ 3 to $<5 \times \text{ULN}$.
- ≥ 5 to $<8 \times \text{ULN}$.
- $\geq 8 \times \text{ULN}$.

TBL:

- $<1 \times \text{ULN}$ (or below the LLOQ).
- ≥ 1 to $<2 \times \text{ULN}$.
- $\geq 2 \times \text{ULN}$.

Occurrences of AST or ALT $\geq 3 \times \text{ULN}$ together with TBL $\geq 2 \times \text{ULN}$ are reported as SAE (Potential Hy's Law).

Platelet count

Platelet count will be classified as follows:

- $< \text{LLN}$
- $> \text{ULN}$

- < 50 ($10^9/L$)
- < 75 ($10^9/L$)
- < 100 ($10^9/L$)
- < 150 ($10^9/L$)
- > 30% decrease from baseline
- < 150 ($10^9/L$) and > 30% decrease from baseline

Shift to minimum value on-treatment value for platelet count will be classified as follows:

- < 50 ($10^9/L$)
- ≥ 50 and < 75 ($10^9/L$)
- ≥ 75 and < 100 ($10^9/L$)
- ≥ 100 and < 150 ($10^9/L$)
- ≥ 150 ($10^9/L$)

Missing data will not be imputed and only observed values will be reported in the summary tables and listings. Treatment discontinuation visit will be mapped according to Section 3.3.2.

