4.3.3.2 Presentation

Laboratory data will be summarized based on the Safety Analysis Set. Summaries of the individual values and change from baseline will be presented by treatment group and visit according to the principles outlined in section 3.3.1. The number and proportion of patients with liver enzyme abnormalities will be summarized by treatment group and visit including a summary of the maximum recorded post-baseline value. Treatment-emergent platelet count abnormalities will be summarised by treatment group and visit, including the shift to minimum value and key subject information will be presented.

Shift tables will be presented for select laboratory parameters (clinical chemistry and hematology). An additional shift table will be presented for hematology results, displaying the percent change from baseline (i.e. the relative change). Spaghetti plots over time will be produced for platelet count, ALT, AST, and TBL, with the corresponding reference range overlaid on top. The following additional plots will be presented for platelet count only:

- Empirical cumulative distribution function curves for the absolute change from baseline to minimum value.
- A spaghetti plot of the relative change from baseline in subjects with platelet count <150 ($10^9/L$) or $> 30\%$ decrease from baseline.
- A spaghetti plot of the absolute change from baseline in subjects with platelet count <150 ($10^9/L$) or $> 30\%$ decrease from baseline.

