5 INTERIM ANALYSIS

After all randomized patients have completed (or discontinued from) the treatment period, an interim analysis will be performed for all endpoints except for PK variables. Efficacy outputs will display visits up to and including the Week 12 time point, all visits will be displayed for the safety outputs.

A limited number of Sponsor personnel will be unblinded at the time of interim analysis. Investigators, participants and site-staff will not be informed of assigned treatment or the results of the interim analysis in order to maintain study integrity. A Confidentiality List/Communication Plan will be prepared documenting unblinded personnel.

This interim analysis will be documented as an interim clinical study report.

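### By-visit liver, platelet and ADA percentages are divided by the whole analysis set rather than by participants with a value at that visit, so every category is deflated and arms with unequal missingness are not comparable.

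*SAP*

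**What the plan says.** Section 3.3 of the Part B SAP sets the default. Unless stated otherwise, "percentages will be calculated using the relevant analysis set population total as the denominator". Section 3.3 of the Part A and Part C SAPs carries the same rule.

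Safety tables use the Safety Analysis Set. In Part B (3.2.4) this is everyone randomised "who took at least one dose of study intervention and for whom any post-dose data are available". A value at any particular visit is not required.

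Three kinds of categorical table are planned by visit:

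- **Liver enzymes.** Part B 4.3.3.2: "The number and proportion of patients with liver enzyme abnormalities will be summarized by treatment group and visit". Part A 4.2.3.4 and Part C 4.2.3.4 plan the same.
- **Platelets.** Part B 4.3.3.2: "Treatment-emergent platelet count abnormalities will be summarised by treatment group and visit". Part A 4.2.3.4 (reduced platelet count) and Part C 4.2.3.4 correspond.
- **ADA positivity.** Part A 4.2.9.4, Part B 4.2.6.4 and Part C 4.2.9.4 tabulate number and percentage positive by visit and arm.

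None of these sections names another denominator. Part B 4.1.1.2 does name one for subject disposition (subjects randomised), so the authors stated exceptions where they wanted them.

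On missing laboratory data, Part B 4.3.3.1 says: "Missing data will not be imputed and only observed values will be reported". It does not mention the denominator. For the Part B interim analysis, SAP section 5 says that "all visits will be displayed for the safety outputs". Protocol 9.5 places the data cut-off where all participants have completed 12 weeks (Visit 10).

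**The concern.** A by-visit abnormality rate is normally read as the share of participants measured at that visit who were abnormal. Under the default rule it is the share of everyone in the safety set, measured or not. The same SAPs summarise continuous variables with the number of non-missing observations. For one ALT dataset at one visit, the mean could rest on 18 participants and the category percentages on 20.

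The late follow-up visits are most exposed. At the Part B interim, Weeks 14 to 24 will not yet be due for participants randomised late, yet those visits are displayed. SAP Part B 3.1 says sponsor personnel are unblinded at this analysis to support Phase 3 planning and possible regulatory interaction, and section 5 says it is reported as an interim CSR. A liver or platelet rate that looks low only because many participants have not reached the visit could be misread there. If one arm has more missing values than another, part of the printed difference between arms reflects missingness.

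**Working it through.** **The plan's own figure.** The documents state no by-visit abnormality rate. The nearest figure is the dropout allowance in Protocol 9.2: 18 evaluable per arm with 10% dropout gives 18/0.90 = 20 per arm, and 3 × 20 = 60. This matches the stated 60. The 10% allows for evaluability of the LDL-C endpoint, so using it for laboratory missingness is an assumption.

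**Formula.** Let N be the arm's analysis-set total, n_v the number with a value at visit v, and x the number in a category.

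- Printed percentage = x/N
- Observed-case percentage = x/n_v
- Printed ÷ observed = n_v/N, so the relative understatement is 1 − n_v/N

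The ratio does not depend on x, so it applies to normal and abnormal categories alike. The liver classes are exclusive and exhaustive, so their printed percentages sum to n_v/N, for example 18/20 = 90%. The Part B and Part C platelet classes overlap and offer no such check.

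**Part B, N = 20 per arm** (all randomised assumed to be in the safety set):

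| No value at visit | n_v/N | x | Observed case | Printed |
|---|---|---|---|---|
| 0 | 1.00 | 3 | 15.0% | 15.0% |
| 2 | 0.90 | 1 | 5.6% | 5.0% |
| 2 | 0.90 | 2 | 11.1% | 10.0% |
| 2 | 0.90 | 3 | 16.7% | 15.0% |
| 4 | 0.80 | 2 | 12.5% | 10.0% |
| 4 | 0.80 | 3 | 18.8% | 15.0% |
| 10 | 0.50 | 2 | 20.0% | 10.0% |

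The row with 2 missing uses the protocol's 10%. The rows with 4 and 10 missing are assumptions. The last represents half an arm not yet at a late follow-up visit at the interim cut-off.

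**Comparison of arms, hypothetical counts with 4 missing in one arm only:**

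- Missing on active: active 2/16 = 12.5%, placebo 1/20 = 5.0%, difference 7.5 points. Printed: 10.0% − 5.0% = 5.0 points, so the difference shrinks.
- Missing on placebo: active 3/20 = 15.0%, placebo 2/16 = 12.5%, difference 2.5 points. Printed: 15.0% − 10.0% = 5.0 points, so the difference widens.

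**Parts A and C (8 active, 3 placebo).** With one active participant missing, 1/7 = 14.3% prints as 1/8 = 12.5%. With one placebo participant missing, 1/2 = 50% prints as 1/3 = 33%.

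**Limit of the change.** Suppose 3 of 20 become abnormal and all 3 then stop attending. The later visit shows 0/20 under the current rule and 0/17 under an observed-case rule. Both print zero.

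**The case against.** The other side's best case is that these tables are descriptive and untested, and that the effect is small. At 10% missing it is 0.6 to 1.7 percentage points for 1 to 3 events. Counts stand beside the percentages, and the by-visit summaries of laboratory values print the non-missing number, so a reader can recompute. Maximum post-baseline liver values, the platelet minimum, spaghetti plots and listings do not use a visit denominator, so no individual case is lost. Protocol 7.1 asks participants who stop treatment to keep attending for three months, which limits missingness. The final analysis later repeats the interim scope with complete follow-up.

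Most of this stands and limits the weight of the point. It does not make the printed percentage right. Recomputation is also harder for ADA: titre is summarised only for positive samples, so the planned ADA table need not show how many were tested. The Part B figure of percentage ADA-positive over time would inherit the same denominator.

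A reader might go further in four ways that the documents do not support:

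- *Missing participants are counted as normal.* They enter no class, and the lowest liver class is deflated too. No value is imputed in these tables. Part B 4.2.6.2 does treat missing ADA results as negative, but for the derived ADA categories, which is a separate matter.
- *The active–placebo difference is always understated.* The direction depends on which arm has missing values, and the documents do not say.
- *QTcF outliers and reference-range flags are affected in the same way.* The outliers are to be tabulated and the flags derived, but neither is expressly given as a by-visit percentage table.
- *Unscheduled samples are certain to add to the missingness.* Section 3.3.3 says "The values measured at unscheduled visits will not be included in the by-visit summary tables", but 3.3.2 describes exhaustive analysis windows assigned by actual date. That tension needs its own clarification.

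**Conclusion.** The point holds for the by-visit liver, platelet and ADA-positivity tables in all three SAPs. The stated default gives percentages that equal the observed-case percentage times n_v/N. The relative deflation is 10% if 10% of an arm have no value, 20% if 20% have none, and nothing if all are measured. For Weeks 14 to 24 of the Part B interim safety tables it could reach 50% if half an arm has no value yet. That share is assumed, because the documents give neither missingness by visit nor the recruitment pace. Arms with unequal missingness cannot be compared on the printed percentages, and the distortion can run either way.

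The primary efficacy analysis, AE tables and any-time extreme-value summaries are untouched. This is a reporting rule worth correcting before the tables are relied on, not evidence that a safety signal would be hidden.

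**What to change.** Add one sentence to section 3.3 of each SAP: by-visit categorical safety and ADA summaries use as denominator the number of participants in the analysis set with a non-missing value at that visit, printed as n/m (%). Apply the same denominator to the Part B figure of ADA positivity over time. Keep the analysis-set total for AE tables and any-time summaries.

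The cost is one sentence per SAP and one extra column in the affected table shells. No new data or model is needed.

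The change corrects the percentage and makes missingness visible at each visit. It does not remove selection: participants who leave after an abnormal result drop out of later numerators under either rule. A table footnote should therefore direct readers to the any-time maximum and minimum summaries alongside the by-visit rates.

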3.3.1 General Study Level Definitions

3.3.1.1 Definition of Baseline

Unless otherwise specified, ‘baseline’ refers to the last measurement obtained before the first dose of study intervention. For lipid parameters (PCSK9, LDL-C, etc), the measure taken pre-dose at Visit 3 (Day 1) will be typically considered as baseline.

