12-lead ECG ^c	X		X	X		X		X		X	X ^j	X	Section 8.2.3
Serum chemistry	X		X	X	X	X	X	X	X	X	X	X	Section 8.2.4
Hematology	X		X	X	X	X	X	X	X	X	X	X	Section 8.2.4
Coagulation parameters	X		X	X	X	X	X	X	X	X	X	X	Section 8.2.4
hs-CRP	X		X					X		X	X	X	Section 8.2.4
Complement activation panel ^d			X			X		X					Section 8.2.4
Urinalysis	X		X	X	X	X	X	X	X	X	X	X	Section 8.2.4
Urine renal safety biomarkers	X		X	X	X	X	X	X	X	X	X	X	Section 8.2.4
Pharmacodynamics													
LDL-C ^e		X	X	X	X	X	X	X	X	X	X	X	Section 8.5.3.1
PCSK9 ^e		X	X	X	X	X	X	X	X	X	X	X	Section 8.5.3.1

Table 2 Schedule of Activities (Part B)

	Screening		Treatment Period							EDV	Follow-up period ⁿ	Final Follow-up Visit ⁿ	Corre-sponding Section in Protocol
Visit Number	1	2	3	4	5	6	7	8	9		10, 11, 12, 13, 14, 15	16	
Study Week			0	1	3	4	6	8	10		12, 14, 16, 18, 20, 22	24	
Study Day	Days -28 to -10	Days -7 to -4	Day 1	Day 8	Day 22	Day 29	Day 43	Day 57	Day 71		Days 85, 99, 113, 127, 141, 155	Day 169	
Visit Window				± 1 day	± 2 days		± 2 days	± 2 days					
Triglycerides ^e		X	X	X	X	X	X	X	X	X	X	X	Section 8.5.3.1
Other lipid parameters ^e			X	X	X	X	X	X	X	X	X	X	Section 8.5.3.1
Pharmacokinetics													
Plasma sample for total full length ASOs of AZD8233 ^f				X		X	X	X	X	X	X ^f	X	Section 8.5.1
Immunogenicity													
Samples for anti-AZD8233 antibodies ^g			X	X		X		X		X	X ^g	X	Section 8.5.2
Exploratory biomarker analysis													
Biomarker analyses (plasma) ^e	X		X	X	X	X	X	X	X	X	X	X	Section 8.6.1
Biomarker analyses (urine) ^e			X	X	X	X	X	X	X	X	X	X	Section 8.6.1
Genomics Initiative optional, exploratory genetic sample ^h			X										Section 8.7

ADA = antidrug antibody; BMI = body mass index; D = day; ECG = electrocardiogram; EDV = early discontinuation visit; FSH = follicle-stimulating hormone; HbA1c = haemoglobin A1c; hs-CRP = high sensitive C-reactive protein; LDL-C = low-density lipoprotein cholesterol; LH = luteinizing hormone; PCSK9 = proprotein convertase subtilisin/kexin type-9; PK = pharmacokinetic; IMP = Investigational medicinal product

Subjects are required to be fasted for at least 10 hours overnight prior to all study visits except for Visit 1; subjects are permitted to drink water during this period of fasting until 1 hour before blood sampling. On days when subjects attend the clinic in a fasting state, blood and urine samples should be obtained prior to administration of the IMP.

Samples to be obtained from all treatment arms unless specified in the table.

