10 Males must be surgically sterile or using, in conjunction with their female partners, a highly effective method of contraception for the duration of the study (from the time they sign consent) and for 3 months after the final follow-up visit to prevent pregnancy in a partner. Acceptable methods of contraception include birth control pills, injections, implants, or patches, intrauterine devices (IUDs), tubal ligation/occlusion, and vasectomy. A barrier method is not necessary if the female partner is sterilized. Male study participants must not donate or bank sperm during this same time period.

Rationale for LDL-C upper limit:

Based on the reference value of LDL hypercholesterolemia, as proposed by the Japan Atherosclerosis Society (JAS) guidelines.

Informed consent

- 11 Capable of giving signed informed consent as described in [Appendix A](#) which includes compliance with the requirements and restrictions listed in the informed consent form (ICF) and in this protocol.
- 12 Provision of signed and dated, written informed consent form prior to any mandatory study specific procedures, sampling, and analyses.

[Part B]

Age

- 1 Participants must be 20 to 75 years of age inclusive, at the time of signing the informed consent.

Type of Participant and Disease Characteristics

- 2 Have a fasting LDL-C \geq 70 mg/dL but < 190 mg/dL at screening (Visit 2).
- 3 Have fasting triglycerides < 400 mg/dL at screening (Visit 2).

- 4 Should be receiving statin therapy as defined in [Appendix H](#), in accordance with the Japan Atherosclerosis Society (JAS) guidelines for prevention of atherosclerotic cardiovascular diseases.
- 5 LDL-lowering medications should be on stable dosing for ≥ 3 months prior to screening with no planned medication or dose change during study participation. The exception to this restriction is for fenofibrate; if the participant is receiving fenofibrate, the therapy must be stable for at least 6 weeks prior to randomization at a dose that is appropriate for the duration of the study in the judgement of the Investigator. Other fibrate therapies (and derivatives) are prohibited. Non-LDL-lowering medications should be on stable dosing for ≥ 3 months prior to screening with no planned medication or dose change during treatment period.
- 6 Have suitable veins for cannulation or repeated venepuncture.

Weight

- 7 BMI between 19 and 40 kg/m²

Sex

- 8 Male or female

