Follow-up visits (Visits 10-16): At all follow-up visits, ECG and an abbreviated physical examination are required, and vital signs, blood, and urine samples are to be checked.

An ADA sampling is to be performed at Visit 10 (Week 2 after last dose; \pm 2 days). At all follow-up visit PK sampling is to be performed.

Early Discontinuation Visit: The EDV may take place any time during the study, in case a participant discontinues study treatment prior to Visit 9 (where last dose of study treatment is administered). The same assessments as done during the final follow-up visit will be performed. See Section 7.1.

Final follow-up visit (Visit 17): The final follow-up visit will be performed in Week 16 after last dose (\pm 2 days). PK and ADA sampling is to be performed. A complete physical examination must be performed on the visit, and body weight, BMI, vital signs, body temperature, and ECG are to be checked. Blood and urine sampling is to be obtained.

The maximum blood volume to be drawn from each participant will not exceed 800 mL over the duration of the study period. Repeat or unscheduled samples may be taken for safety reasons or for technical issues with the samples.

[Part B]

Visit 1 (enrollment) and Visit 2: At Visit 1 (Day -28 to Day -10), participants will be asked to sign the informed consent and optional informed consent for future genetic research sample. Participant demographics and medical history, including smoking and alcohol consumption history, will be recorded in the eCRF. A complete physical examination must be

performed. Vital signs, height, weight, BMI, and ECG must be checked, as well as blood and urine sample collection. Visit 2 (Day -7 to Day -4) will include an additional blood sample collection for LDL-C, PCSK9, and triglycerides.

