9.4.1 General Considerations

Unless otherwise stated, the safety analysis set will also be used for the presentation of all demographic data. If not otherwise specified, baseline refers to the last measurement prior to study intervention administration.

Statistical tests will be performed using two-sided test at a 5% significance level, if not explicitly stated otherwise. The SAS® version 9.3 or higher will be used for the data analysis. All results will be presented by treatment with descriptive statistics appropriate to the nature of the variables. Demographic and baseline characteristics will be presented as follows: for continuous variables, the number of non-missing observations, mean, Standard Deviation (SD), Standard Error of the Mean (SEM), 95% Confidence Interval (CI) of the mean, median,

first and third quartiles, minimum and maximum as appropriate ; for categorical variables, counts (n) and percentages (%) (where specified) will be presented. These summaries will be provided by time point of assessment as appropriate.

Baseline for efficacy assessments refers to the last measurements obtained before randomization. Baseline for safety assessments refers to the last measurements obtained before the first dose of IMP.

Primary estimand is hypothetical estimand, if all the patients had continued treatment until Week 12. The primary analysis will be carried out with likelihood based repeated measure model, which would provide unbiased treatment effect under the assumption of Missing At Random. Sensitivity analyses including different type of estimands will be detailed in the statistical analysis plan.

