3.3.1 General Study Level Definitions

3.3.1.1 Definition of Baseline

Unless otherwise specified, ‘baseline’ refers to the last measurement obtained before the first dose of study intervention. For lipid parameters (PCSK9, LDL-C, etc), the geometric mean of the two measures taken pre-dose at Visit 2 (Day -1 and pre-dose Day 1) will be considered as baseline.

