4.2.1.4 Primary Analysis of Primary Endpoint

The analysis and presentation will be based on subjects in the Full Analysis Set.

The study hypothesis to be tested is treatment effect of AZD8233 across different dose levels [REDACTED] compared to placebo. The null hypotheses for these tests are that the absolute change in log-transformed LDL-C for AZD8233 at some dose level is equal to the absolute change in log-transformed LDL-C for placebo.

A mixed model with repeated measures will be fitted using the log-transformed LDL-C data. The model will include the log-transformed LDL-C baseline value as a covariate and time point (visit number), treatment, and the interaction between time point and treatment will be included as factors. The response variable will be change from baseline in log-transformed LDL-C. The model will be fitted with an unstructured covariance structure, and the Kenward-Roger correction applied to obtain the degrees of freedom. The primary model will include data up to and including Week 12 as a response variable.

Estimation of the treatment effect will be calculated for each visit after baseline and presented alongside the corresponding 95% confidence interval. In case of issues when fitting the model to the data, the following hierarchical model fitting procedure will be adopted:

1. The MMRM will be fitted using a spatial power covariance structure; Visit will be expressed as scheduled visit days to accomplish the variance-covariance matrix estimation.
2. The MMRM will be fitted using a compound symmetry covariance structure.
3. An ANCOVA model for Week 12 only will be used.

Comparisons of the change from baseline between the treatment groups will be conducted using the least square mean difference (LSMD) between treatment groups as estimated by

the fitted model. Pair-wise comparisons will be done for each AZD8233 dose [REDACTED] vs. placebo. In addition, pair-wise comparisons between AZD8233 dose groups [REDACTED] will also be done for reference. The p-value for each comparison will be presented alongside the LSMD and its 95% CI. In addition, LSMs and 95% CIs will be back-transformed to present as relative (geometric) difference among treatment groups and the relative change will also be presented as the percent change from baseline.

Change from baseline will be summarized by visit and treatment groups using descriptive statistics (arithmetic mean, SD, minimum, median, maximum) and based on the principles defined in Section 3.3.

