3.3.1 General Study Level Definitions

3.3.1.1 Definition of Baseline

Unless otherwise specified, ‘baseline’ refers to the last measurement obtained before the first dose of study intervention. For all lipid parameters (PCSK9, LDL-C and other lipid parameters listed in Section 4.2.8.1) the geometric mean of the two measures taken pre-dose at Visit 2 (Day -1 and pre-dose Day 1) will be considered as baseline.

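### Part B's MMRM adjusts for a single pre-dose value; adding the already collected Visit 2 value as a second covariate would modestly tighten the estimates

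*SAP*

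**What the plan says.** Part B SAP section 3.3.1.1 sets the lipid baseline: "the measure taken pre-dose at Visit 3 (Day 1) will be typically considered as baseline". Section 4.2.1.4 subtracts it from the response and also adjusts for it: "The model will include the log-transformed LDL-C baseline value as a covariate". No other pre-treatment lipid value enters the model.

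Protocol section 8 states that Part B Visit 2 (Day -7 to Day -4) "will include an additional blood sample collection for LDL-C, PCSK9, and triglycerides". Under the Part B schedule of activities this sample is fasted in the same way as Day 1: "Subjects are required to be fasted for at least 10 hours overnight prior to all study visits except for Visit 1". Inclusion criteria 2 and 3 use the Visit 2 LDL-C and triglycerides for eligibility.

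The Part A and Part C SAPs define the lipid baseline differently: "the geometric mean of the two measures taken pre-dose at Visit 2 (Day -1 and pre-dose Day 1) will be considered as baseline". Protocol section 9.4.1 has one rule for efficacy: "Baseline for efficacy assessments refers to the last measurements obtained before randomization".

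**The concern.** Part B is the only part with hypothesis tests, and its baseline enters the model twice. A single LDL-C or PCSK9 value carries day-to-day biological and assay variation, so it explains less of the Week 12 value than two values would. A second fasted value, taken about a week earlier on stable lipid-lowering therapy, is already in the database but has no role in any model. The descriptive parts average two values, and no reason is given for the difference.

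What is at stake is the width of the Part B intervals, above all for the comparison between the two active doses, since Part B is meant to inform dose selection. Validity is not in question.

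**Working it through.** **Inputs from the documents** (protocol section 9.2): SD 0.3 on the log scale, 18 evaluable per arm, differences of 0.693 (versus placebo) and 0.33 (between doses), two-sided 5% t-test, 10% drop-out, 60 randomised.

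**Inputs assumed.** The documents give no within-person variance or correlation. I take between-person log SD b = 0.20-0.25, within-person log SD w = 0.08-0.15, and SD of individual response on active h = 0.20-0.25 (h = 0 on placebo).

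**1. The plan's own figures.** SE = 0.3 × √(2/18) = 0.100. With 34 degrees of freedom and the noncentral t distribution, power is 89.4% for 0.33 (stated: about 89%) and above 99.99% for 0.693 (stated: more than 95%). The 95% CI half-width is 2.032 × 0.100 = 0.203. Total: 54/0.9 = 60. All reproduce.

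**2. Formula.** With k exchangeable baseline values, the residual variance after adjustment is

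b² + w² + h² − b⁴/(b² + w²/k).

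Subtracting Day 1 from the response does not alter this, because the Day 1 coefficient absorbs it. Two exchangeable covariates receive equal weight at the Week 12 level, so entering both gives the same residual variance as adjusting for their mean (k = 2).

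**3. Worked example** (b = 0.25, w = 0.10, h = 0.25).
- Placebo, k = 1: 0.0725 − 0.003906/0.0725 = 0.0186. With k = 2: 0.0725 − 0.003906/0.0675 = 0.0146.
- Active: add 0.0625, giving 0.0811 and 0.0771.
- Active-placebo sum: 0.0997 to 0.0918, so the SE falls by 1 − √(0.0918/0.0997) = 4.1%.
- Residual variance pooled over three equal arms, as in the planned model, which has no arm-specific covariance: (2 × 0.0811 + 0.0186)/3 = 0.0603 to 0.0563, so the SE falls by 3.4%.

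**4. Over the assumed ranges.**

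| Quantity | Reduction |
|---|---|
| Residual SD, placebo | 7.9% to 12.0% |
| Residual SD, active | 1.7% to 4.5% |
| Active-placebo SE, arm-specific variances | 3.0% to 6.1% |
| SE, variance pooled over arms | 2.4% to 5.5% |

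**5. Cost of the extra coefficient.** With 54 evaluable participants in 3 arms, the expected variance inflation from p covariates is (51 − 1)/(51 − p − 1). Going from one to two gives 49/48 = 1.021, or about 1.0% on the SE. The pooled range of 2.4%-5.5% becomes about 1.4%-4.5% net.

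**6. If Week 12 is weakly tied to baseline.** Let rbb be the correlation between the two baselines and rbp that of baseline with Week 12. The variance ratio is (1 − 2·rbp²/(1 + rbb))/(1 − rbp²). For rbb 0.7-0.9 and rbp 0.2-0.5 the variance falls by only 0.2% to 6%. At the low end the 2.1% inflation in step 5 outweighs it.

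**7. Effect on power.** Scaling SD 0.3 by the pooled range in step 4 gives 0.293 to 0.284. Power for 0.33 is 90.9% at SD 0.292 and 92.5% at SD 0.283, so the dose comparison moves from 89.4% to roughly 91%-92% before the cost in step 5. Power against placebo stays above 99.99%.

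**The case against.** The strongest objection is that Part B does what the protocol says. The pre-dose Day 1 value fits the section 9.4.1 definition. Parts A and C are the ones that depart from it, and neither lists the departure in its SAP section 2. A reader might infer from the contrast that Part B's baseline is wrong and should become the mean of two values. The documents do not support that, for three reasons.

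- **Selection.** Visit 2 LDL-C is the eligibility value, whereas Parts A and C average two samples taken after screening. In a simulation with assumed median 85-100 mg/dL, log SD 0.3 and correlation 0.6-0.8, restricting Visit 2 to 70-190 mg/dL left it 0.01 to 0.05 log units above Day 1 on average. Averaging would shift reported within-arm changes by half of that.
- **Method.** The primary variable is LDL-C with reflex to PUC/beta-quantification. Total cholesterol and HDL-C are not scheduled at Visit 2, and the documents do not say how the Visit 2 LDL-C is obtained.
- **Coverage.** The remaining lipids have no Visit 2 value, so change scores would rest on mixed baseline definitions.

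These stand against putting Visit 2 into the change score. They do not stand against using it as a covariate: the change score keeps its definition, and a covariate measured before randomisation need not share the outcome's assay or be free of selection. In the same simulation the adjusted variance still fell by 9%-17%.

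It is also fair to say that the placebo tests gain nothing in practice, that the dose comparison is labelled as for reference, and that the size rests on assumptions. All of that stands and limits the weight of the point.

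**Conclusion.** The point holds as a minor loss of efficiency. Two fasted pre-randomisation values exist for LDL-C, PCSK9 and triglycerides, and the Part B model uses one. Under the assumed variances the active-placebo SE would fall by about 2%-6% before the cost of the extra coefficient (about 1%). The gain is smaller, and could be nil or slightly negative, if Week 12 is only weakly related to baseline. It would show in interval width and in the dose-versus-dose comparison.

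Two stronger readings should be avoided. The single baseline does not bias the randomised contrasts, since either choice precedes randomisation. Nor does it put the primary tests at risk, because their power exceeds 99.99% under the plan's own inputs.

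**What to change.** Before anyone is unblinded for the Week 12 analysis:

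- Keep Day 1 pre-dose as the protocol-defined baseline for change and percent change.
- In the Part B MMRMs for LDL-C, PCSK9 and triglycerides, add the log Visit 2 value as a second covariate beside the Day 1 value.
- Set a missing Visit 2 value to that participant's Day 1 value.
- Record the addition in Part B SAP section 2.

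The cost is one extra model parameter and one entry in section 2. No new sample or visit is needed. Lipids not sampled at Visit 2 keep the single-covariate model, so the models differ between analytes and the SAP should say so.
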